The sponsor will perform oversight of the data management of this study, including approval of the CRO's data management plans and specifications. Sponsor's standard procedures will be used to handle and process the electronic transfer of these data (including the non eCRF data). The clean database will be transferred to the Sponsor for analysis of the correlations with the clinical or subclinical efficacy and safety profile of the patients included in the substudy.

eCRFs and correction documentation will be maintained in the EDC system's audit trail. System backups for data stored at the Sponsor and records retention for the study data will be consistent with the Sponsor's standard procedures.

Substudy data will be recorded via the instrument used for data acquisition (flow cytometer, luminex technology, sequencing etc.) and for most experiments will be processed by CHU of Nantes to generate key data. These non eCRF data will be handled using the Sponsors standard procedures to handle and process these data.

Source data documentation

The Investigators shall supply the Sponsor on request with any required background data from the substudy documentation or clinic records. This is particularly important when errors in data transcription are suspected. In case of special problems and/or governmental queries or requests for audit inspections, it is also necessary to have access to the complete study records, provided that patient confidentiality is protected.

Use of computerized systems

When clinical observations are entered directly into a study site's computerized medical record system (i.e., in lieu of original hardcopy records), the electronic record can serve as the source document if the system has been validated in accordance with health authority requirements pertaining to computerized systems used in clinical research. An acceptable computerized data collection system allows preservation of the original entry of data. If original data are modified, the system should maintain a viewable audit trail that shows the original data as well as the reason for the change, name of the person making the change, and date of the change.

Retention of records

Records and documents pertaining to the conduct of this substudy, Informed Consent Forms, laboratory test results, and medication inventory records, must be retained by the Principal

Ocrelizumab—F. Hoffmann-La Roche Ltd

151/Protocol MA30143, Version 10.0

Investigator for at least 15 years after completion or discontinuation of the study, or for the length of time required by relevant national or local health authorities, whichever is longer. After that period of time, the documents may be destroyed, subject to local regulations. No records may be disposed of without the written approval of the Sponsor. Written notification should be provided to the Sponsor prior to transferring any records to another party or moving them to another location.

ETHICAL CONSIDERATIONS

Compliance with Laws and Regulations

This study will be conducted in full conformance with the International Conference on Harmonization (ICH) E6 guideline for Good Clinical Practice and the principles of the Declaration of Helsinki, or the laws and regulations of the country in which the research is conducted, whichever affords the greater protection to the individual. The study will comply with the requirements of the ICH E2A guideline (Clinical Safety Data Management: Definitions and Standards for Expedited Reporting). Studies conducted in the United States or under a U.S. Investigational New Drug (IND) application will comply with U.S. Food and Drug Administration regulations and applicable local, state, and federal laws. Studies conducted in the European Union (E.U.) or European Economic Area will comply with the E.U. Clinical Trial Directive (2001/20/EC).

Informed Consent

All patients must sign the informed consent form for the main study (MA30193) prior to screening. Additionally, all patients enrolled in this substudy must sign a separate informed consent form for collection of sample(s) prior to any substudy specific assessments.

The Sponsor's sample Informed Consent Form (and ancillary sample Informed Consent Forms such as a Caregiver Assent Form) will be provided to each site. If applicable, it will be provided in a certified translation of the local language. The Sponsor or its designee must review and approve any proposed deviations from the Sponsor's sample Informed Consent Forms or any alternate consent forms proposed by the site (collectively, the "Consent Forms") before IRB/EC submission.

The investigator or authorized designee will explain to each patient the objectives, methods, and potential risks associated with substudy procedures. Patients will be told that they are free to refuse to participate and may withdraw their consent at any time for any reason. A separate, specific informed consent form will be required to document a patient's agreement to participate in substudy procedures.

The Consent Forms must be signed and dated by the patient or the patient's legally authorized representative before his or her participation in the study. The case history or clinical records for each patient shall document the informed consent process and that written informed consent was obtained prior to participation in the study.

The Consent Forms should be revised whenever there are changes to study procedures or when new information becomes available that may affect the willingness of the patient to participate.

Patients must be re-consented to the most current version of the Consent Forms (or to a significant new information/findings addendum in accordance with applicable laws and IRB/EC policy) during their participation in the study. For any updated or revised Consent Forms, the case history or clinical records for each patient shall document the informed consent process and that written informed consent was obtained using the updated/revised Consent Forms for continued participation in the study.

A copy of each signed Consent Form must be provided to the patient or the patient's legally authorized representative. All signed and dated Consent Forms must remain in each patient's study file or in the site file and must be available for verification by study monitors at any time.

Institutional Review Board or Ethics Committee

This protocol, the Informed Consent Forms, any information to be given to the patient, and relevant supporting information must be submitted to the IRB/EC by the Sponsor and reviewed and approved by the IRB/EC before the study is initiated. In addition, any patient recruitment materials must be approved by the IRB/EC.

The sponsor is responsible for providing written summaries of the status of the study to the IRB/EC annually or more frequently in accordance with the requirements, policies, and procedures established by the IRB/EC. Sponsor is also responsible for promptly informing the IRB/EC of any protocol amendments (see .Section 9.7.).

In addition to the requirements for reporting all adverse events to the Sponsor, investigators must comply with requirements for reporting serious adverse events to the local health authority and IRB/EC. Investigators may receive written IND safety reports or other safety-related communications from the Sponsor. Investigators are responsible for ensuring that such reports are reviewed and processed in accordance with health authority requirements and the policies and procedures established by their IRB/EC, and archived in the site's study file.

Confidentiality

The Sponsor maintains confidentiality standards by coding each patient enrolled in the study through assignment of a unique patient identification number. This means that patient names are not included in data sets that are transmitted to any Sponsor location.

Patient medical information obtained by this study is confidential and may be disclosed to third parties only as permitted by the Informed Consent Form (or separate authorization for use and disclosure of personal health information) signed by the patient or the patient's legally authorized representative, unless permitted or required by law.

Medical information may be given to a patient's personal physician or other appropriate medical personnel responsible for the patient's welfare, for treatment purposes.

Given the complexity and exploratory nature of the analyses, data derived from exploratory biomarker specimens will generally not be provided to study investigators or patients unless required by law. The aggregate results of any conducted research will be available in accordance with the effective Roche policy on study data publication (see .Section 9.6.).

Data generated by this study must be available for inspection upon request by representatives of national and local health authorities, Sponsor monitors, representatives, and collaborators, and the IRB/EC for each study site, as appropriate.

Financial Disclosure

Investigators will provide the Sponsor with sufficient, accurate financial information in accordance with local regulations to allow the Sponsor to submit complete and accurate financial certification or disclosure statements to the appropriate health authorities. Investigators are responsible for providing information on financial interests during the course of the study and for 1 year after completion of the study (i.e., last patient last visit).

STUDY DOCUMENTATION, MONITORING, AND ADMINISTRATION

Study Documentation and record keeping

The investigator must maintain adequate and accurate records to enable the conduct of the study to be fully documented, including, but not limited to, the protocol, protocol amendments, Informed Consent Forms, and documentation of IRB/EC and governmental approval.

Site Inspections

Site visits will be conducted by the Sponsor or an authorized representative for inspection of study data. The investigator will permit national and local health authorities; Sponsor monitors, representatives, and collaborators; and the IRBs/ECs to inspect facilities and records relevant to this study.

Administrative Structure

This trial will be sponsored by Roche, and will be managed by Roche and CROs. CROs will provide clinical operations management, data management, biostatistics, and medical monitoring.

Publication of Data and Protection of Trade Secrets

Regardless of the outcome of a trial, the Sponsor is dedicated to openly providing information on the trial to healthcare professionals and to the public, both at scientific congresses and in peerreviewed journals. The Sponsor will comply with all requirements for publication of study results. For more information, refer to the Roche Global Policy on Sharing of Clinical Trials Data at the following Web site:

http://www.rochetrials.com/pdf/RocheGlobalDataSharingPolicy.pdf

The results of this substudy may be published or presented at scientific congresses. For all clinical trials in patients involving an IMP for which a marketing authorization application has been filed or approved in any country, the Sponsor aims to submit a journal manuscript reporting primary results. If interim analysis of core study is done, correlation with substudy in a separate statistical report might be envisioned. In addition, for all clinical trials in patients involving an IMP for which a marketing authorization application has been filed or approved in any country, the Sponsor aims to publish results from analyses of additional endpoints and exploratory data that are clinically meaningful and statistically sound.

The investigator must agree to submit all manuscripts or abstracts to the Sponsor prior to submission for publication or presentation. This allows the Sponsor to protect proprietary information and to provide comments based on information from other studies that may not yet be available to the investigator.

In accordance with standard editorial and ethical practice, the Sponsor will generally support publication of multicenter trials only in their entirety and not as individual center data. In this case, a coordinating investigator will be designated by mutual agreement.

Authorship will be determined by mutual agreement and in line with International Committee of Medical Journal Editors authorship requirements. Any formal publication of the study in which contribution of Sponsor personnel exceeded that of conventional monitoring will be considered as a joint publication by the investigator and the appropriate Sponsor personnel.

Any inventions and resulting patents, improvements, and/or know-how originating from the use of data from this study will become and remain the exclusive and unburdened property of the Sponsor, except where agreed otherwise.

Ocrelizumab—F. Hoffmann-La Roche Ltd

154/Protocol MA30143, Version 10.0

Protocol amendments

Any protocol amendments will be prepared by the Sponsor. Protocol amendments will be submitted to the IRB/EC and to regulatory authorities in accordance with local regulatory requirements.

Approval must be obtained from the IRB/EC and regulatory authorities (as locally required) before implementation of any changes, except for changes necessary to eliminate an immediate hazard to patients or changes that involve logistical or administrative aspects only (e.g., change in Medical Monitor or contact information).

Appendices to Appendix 8

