6.4 EFFECTIVENESS ANALYSES

6.4.1 Effectiveness Endpoints

Effectiveness of ocrelizumab will be evaluated by means of a set of endpoints addressing different facets of MS. There is no primary endpoint defined in the main study. These effectiveness endpoints include time to onset of confirmed CDP sustained for at least 24 and 48 weeks, change from baseline in EDSS score over time, relapse rates, MRI-based measures of disease activity and progression or degeneration, measures of cognition and PROs.

For a full list of effectiveness endpoints refer to Section 2.

After the Week 192 visit of the last enrolled patient, approximately 24 weeks and 48 weeks may be needed to allow the confirmation of the last event of the 24-week and 48 week-CDP (CDP/CDI confirmation visit). The main study analysis will be performed after the last CDP and CDI confirmation visit. With respect to CDP confirmation visits, only EDSS data at all the visits occurring in the treatment period of the study and LTE study (for patients who roll over to study MN39158) will be used. Appropriate statistical methods to account for missing confirmation visits will be defined in the SAP.

The evaluation of the clinical effectiveness of ocrelizumab will be based upon the events and assessments in-between baseline and week 192.

For patients who do not have an event by week 192, the time-to-event endpoints will be censored at the time of last visit in the study. A descriptive analysis based on the Kaplan-Meier method will be performed for the time to CDP and other time-to-event endpoints, such as the time to first relapse or the time to first event of disease activity. Cox proportional hazards regression will be used to identify predictors for CDP and other time-to-event endpoints. Variables to be included in the regression model will be region, gender, baseline EDSS, and some other variables, as appropriate. Further details will be specified in the SAP.

The change from baseline in EDSS, as well as other continuous variables, will be primarily analyzed using descriptive statistics, the mean, corresponding 95% CI, standard deviation and other statistics will be presented. Furthermore, the change of EDSS from baseline to each visit will be analyzed by linear mixed models for repeated measures (MMRM) adjusting for covariates such as the respective baseline score, geographical region, and baseline EDSS.

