	Thresholds mentioned for B cells analysis may be adjusted according to investigators decision and sampling procedures. In any cases, all analyses will describe the initial cell frequencies in study samples.
	Indirect impact of ocrelizumab-dependent B cell depletion on B cell subsets and functions in naïve RRMS patients will be measured by change from baseline for each marker and for each time point.

Objectives	Corresponding endpoints
Second objective:	
To assess the potential relationship between immunological biomarkers	 Relationship between any B cells subset, CD4⁺ or CD8⁺ T cell subset or immunological marker at baseline, 24, 48, 192 weeks or earlier in case of withdrawal from the study of ocrelizumab treatment or during relapses and core study efficacy and safety objectives of MA30143 core study (endpoints). For instance, neurological markers that will be correlated with interesting immunological markers identified in the first part, will include, but will not be limited to:
levels and clinical and/or	 Total number of T1 Gd-enhancing lesions as detected by brain MRI over time
subclinical change	 Total number of new and/or enlarging T2 lesions as detected by brain MRI over time
assessed by	- Change in T1 volume over time
neurological markers in naïve	 Change in brain volume (including white and grey matter fractions) as detected by brain MRI over time
RRMS patients	- Time to first relapse
treated with	- Change from baseline in EDSS score over the course of the study
ocrelizumab.	Relationship between any biomarkers with any other biomarker.

Study Design

Description of Study

This substudy is a longitudinal, multi-center, substudy of the Phase IIIb ocrelizumab trial MA30143.

This substudy will evaluate the indirect impact of ocrelizumab-dependent B cell depletion on T and B cell subsets and functions in naïve RRMS patients, during B cell depletion and during B cell repletion period off ocrelizumab.

This substudy will help to assess the potential relationship between immunological biomarkers levels and clinical and/or subclinical change assessed by neurological markers in naïve RRMS patients treated with ocrelizumab.

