No IMP is specifically distributed for this substudy. In core MA30143 protocol, the first dose of ocrelizumab will be administered as two 300-mg IV infusions (600 mg total) in 250 mL 0.9% sodium chloride each separated by 14 days (i.e., Days 1 and 15), followed by one 600-mg IV infusion in 500 mL 0.9% sodium chloride every subsequent doses (i.e., every 24 weeks ±14 days) for a maximum of 8 doses.

Statistical Methods

Due to the small sample size, the substudy data analysis will be descriptive only.

If relevant, calculated confidence intervals will be displayed with a 95% level.

Indirect impact of ocrelizumab-dependent B cell depletion on T cell and B cell subsets and functions in naïve RRMS patients will be measured by the change from baseline for each marker and for each time point.

Relationship between biomarkers will be evaluated using correlation coefficient at each endpoint (linear and non-linear correlation will be searched).

Relationship between any B cells or T cell subsets (or any immunological marker at any time point) and core study efficacy and safety objectives will be performed using a regression model to evaluate biomarkers predictive factors of efficacy or safety objectives.

Full details of the derivations and analyses of exploratory endpoints will be detailed in the corresponding substudy Statistical Analysis Plan.

Substudy Design

** B cell numbers SLLN, but sufficient to perform some experiments

X repleting* and partially** repleting patients off ocrelizumab

Visit	Scree ning		Т	reatmen	t Period		Unscheduled Visits		
	1	2 (Base- line)	5	6	12	Early study treatment disconti- nuation visit	Safety Follow-up period	relapse 1	relapse 2
Week	-4 to - 1 wks	1	24 (±14 days)	48 (±14 days)	192 (±14 days)		Visits Every 24 weeks (+/- 14 days) (for 48 weeks after last dose)		
Substudy Inform Consent	х								
Blood Collection for Substudy		x	х	х	х	X (if applicable)	X (if applicable)	X (if applicab le)	X (if applicabl e)

Schedule of Assessments

LIST OF ABBREVIATIONS AND DEFINITIONS OF TERMS

Abbreviation	Definition
ARR	Annualized Relapse Rate
BRC	Biological Resource Center
CD	Cluster of Differentiation
CDP	Confirmed Disability Progression
CHU	Centre Hospitalier Universitaire (University Hospital)
CI	Confidence Interval
CNS	Central Nervous System
CPT	Cell Preparation Tube
CSF	Cerebro-Spinal Fluid
EAE	Experimental Autoimmune Encephalomyelitis
EDSS	Expanded Disability Status Scale
FC	Flow Cytometry
FSS	Functional Systems Score
HC	Healthy Control

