The number of patients that will withdraw from the study is estimated to be 10 (20% withdrawal rate over 192 weeks). As a consequence, approximatively 10 patients would enter the follow-up period for B cell repletion. Patients will provide blood samples every 24 weeks *for 48 weeks* after *the* last ocrelizumab infusion.

Overview of study design

Figure 1 presents an overview of the substudy procedures. A schedule of assessments is provided in Appendix 1..

Figure 1 Overview of Study design

Procedure in case of visit for relapse

In case of unscheduled visit due to a core protocol defined relapse between the weeks 24 and 192 of the study, additional blood sample will be collected ($12 \times 8mL$). This additional blood collection will not occur more than two times for a patient. Extra blood samples will not be collected in case of relapse within the first 24 weeks or during the follow-up.

End and length of substudy

The end of the substudy is defined as the last patient visit *in the Safety Follow-up period or last patient Week 192 visit, whichever occurs later.*

The maximum length of the study, from first patient screening to the end of the substudy, is expected to be approximatively *316* weeks (6.5 years). This includes an enrolment period of approximately 76 weeks.

Centers

The substudy will take place in France, in centers associated with an investigator centers with PBMC technical and storage capacity which can prepare samples for storage, using a similar standardized protocol in all the centers (see Appendix 2). Frozen samples will be shipped to the CHU of Nantes where they will be analyzed.

MATERIALS AND METHODS

Patients

Patients with early stage RRMS who fulfill eligibility criteria for the Phase IIIb study (MA30143) and the eligibility criteria outlined in the following inclusion and exclusion sections of this substudy can be enrolled into the substudy. Approximately 50 patients are planned to be enrolled in the substudy.

Inclusion Criteria

Patients must meet the following criteria to be eligible for substudy entry:

- Enrolled in the Phase IIIb study MA30143
- Signed Informed Consent Form for the MA30143-T and B cell Substudy
- Able to comply with the substudy protocol, in the investigator's judgment.

Exclusion Criteria

There is no exclusion criteria beyond those listed in the main protocol of the MA30143 study.

Substudy assessments

Procedure for enrolment of eligible patients

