The Sponsor has the right to terminate the main study or to close a site at any time. Reasons for termination are listed in the main study protocol (MA30143). The Sponsor will notify the investigators if the Sponsor decides to discontinue the study. Consequently, the substudy could be stopped.

The Sponsor has also the right to terminate this substudy at any time.

The Sponsor will notify the investigator if the Sponsor decides to discontinue the substudy.

ASSESSMENT OF SAFETY

Safety assessment

Adverse events related to the substudy procedure will be collected throughout the substudy according the same procedure of the main study protocol, as outlined in the main study protocol (MA30193).

Blood draw may have procedural adverse events such as minor discomfort, lightheadedness, or bruising at the draw site. If any AE occurs in regards to the procedure for this substudy sample, it should be reported according to the main study protocol instructions in Sections .5.3 and .5.4.

Safety instructions and guidance

Safety measures regarding the study medication are not part of this substudy, and are detailed in the main protocol (MA30143).

Reporting of Adverse Events

If an adverse event specifically related to the substudy procedure occurs, it will be recorded in the e-CRF and documented in the study report.

Reporting of Serious Adverse Events

Refer to Section 5.4.2. of main protocol.

Emergency Medical Contacts

Refer to Section 5.4.1 of main protocol.

STATISTICAL CONSIDERATIONS AND ANALYSIS PLAN

Due to the small sample size, the substudy data analysis will be descriptive only.

The number of patients expected to participate in this optional substudy is \sim 50.

Estimation for a proportion of 50%, with a study size of 50, the precision of the estimation is 13.9%.

If relevant, calculated confidence intervals will be displayed with a 95% level.

All variables will be summarized in statistical tables including the following descriptive statistics:

- The quantitative variables will be described using the number of non-missing values, the number of missing values, the mean, the standard deviation, the median, the first and the third quartiles, the minimum and the maximum.
- The qualitative variables will be described using the number of non-missing values, the number of missing values, the frequency and the percentage per modality.

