Full details of the derivations and analyses of exploratory endpoints will be detailed in the corresponding substudy Statistical Analysis Plan (SAP). The SAP will be written by the Sponsor in accordance with the investigator coordinator of this substudy.

These data are intended to be hypothesis-generating, and are not expected to achieve statistical significance. Data generated as part of this substudy will be described in a separate clinical study report.

Evaluation of the impact of ocrelizumab-dependent B cell depletion on T and B cell subsets and functions in naïve RRMS patients, during B cell depletion and during B cell repletion period off ocrelizumab at the end of the treatment will be measured by the change from baseline for each marker and for each time point.

Assessment of the potential relationship between immunological biomarkers levels and clinical and/or subclinical change assessed by neurological markers will be measured using:

- Correlations between immunological markers and clinical outcome tested using linear and non-linear correlation coefficient.
- Relationship between any B cell subset, CD4⁺ or CD8⁺ T cell subsets (or any immunological marker at any time point) and core study efficacy objectives performed using a regression model to evaluate biomarkers predictive factors of efficacy or safety objectives.

Any additional exploratory analysis might be conducted and will be discussed with the investigator coordinator of this substudy before being described in the SAP

DATA COLLECTION AND MANAGEMENT

Data collection and management

The overall procedures for quality assurance of clinical study data are described in the Sponsor's (or designee's) Standard Operational Procedures.

A contract research organization (CRO) will be responsible for data management of this substudy, including quality checking of the data. Data entered manually will be collected via EDC through use of eCRFs (e.g. informed consent, withdrawal of consent, sample collection dates). Investigators will be responsible for data entry into the EDC system. In the event of discrepant data, the CRO will request data clarification from the site, which the site will resolve electronically in the EDC system.

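### Appendix 8 plans to relate immune markers to time to first relapse with correlation coefficients, which cannot take account of censoring

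*Protocol*

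**What the plan says.** Under the second objective of Appendix 8, both the synopsis and the body introduce "neurological markers that will be correlated with interesting immunological markers identified in the first part". The illustrative list that follows includes "Time to first relapse", next to MRI lesion counts, T1 volume, brain volume and EDSS change.

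The Statistical Considerations section of Appendix 8 gives two methods for this objective. The first bullet is "Correlations between immunological markers and clinical outcome tested using linear and non-linear correlation coefficient". The second is a relationship between cell subsets and core efficacy objectives, "performed using a regression model to evaluate biomarkers predictive factors of efficacy or safety objectives". The type of regression is not named, and Appendix 8 has no censoring rule.

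The Statistical Methods part of the Appendix 8 synopsis divides the work differently: "Relationship between biomarkers will be evaluated using correlation coefficient at each endpoint", with regression assigned to the core efficacy and safety objectives.

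In the main protocol, Section 6.4.1 says that for patients without an event by Week 192 "the time-to-event endpoints will be censored at the time of last visit in the study". The same section uses Cox regression to look for predictors of time-to-event endpoints.

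**The concern.** Time to first relapse is known exactly only for patients who relapse. For the rest, the recorded time is a lower bound, set by Week 192 or by withdrawal. A correlation coefficient works on the recorded number alone, so someone who leaves relapse-free at Week 60 counts the same as someone who relapses at Week 60.

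Two things follow. Withdrawal adds noise that weakens a real association between marker and relapse. And if a marker is related to withdrawal, the coefficient picks up that relation and presents it as one with relapse.

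The second point is not far-fetched. The re-treatment criteria in Section 3.1.3 include a CD4 threshold, CD4+ T cells are a core marker of this substudy, and Section 3.1.4 discontinues patients who begin another MS treatment. So a route from marker to censoring exists. How often it operates is unknown.

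What is at stake is the list of candidate markers. Even for generating hypotheses, a ranking that partly reflects withdrawal is not the ranking wanted.

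**Working it through.** **The plan's own figure.** The only sizing figure in Appendix 8 is the precision of a 50% proportion with 50 patients: 1.96 × √(0.5 × 0.5 / 50) = 0.1386, which reproduces the stated 13.9%. No power, test level, relapse rate or effect size is given for the marker analyses.

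**Inputs from the documents.** About 50 patients; 10 withdrawals (50 × 0.20) over 192 weeks (Appendix 8, description of the substudy); censoring at last visit (Section 6.4.1).

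**Assumptions.** Relapse risk by Week 192 of 10% to 50%; hazard ratio 2 per SD of a standard normal marker (range 1.5 to 3.0); exponential relapse and withdrawal times; administrative censoring at about Week 192; two-sided 5% tests.

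**How much is censored.** With no marker effect, the simulated mean number of observed relapses is 4.5, 9.0, 13.6 and 22.8 at relapse risks of 10%, 20%, 30% and 50%. The censored share is therefore 45.5/50 = 91%, 41/50 = 82%, 36.4/50 = 73% and 27.2/50 = 54%. At 10-20% relapse, withdrawals are about as numerous as relapses or more so, and they supply much of the spread in recorded times.

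**Power when withdrawal is unrelated to the marker (hazard ratio 2 per SD).** Relative loss is 1 − (correlation power / Cox power). The Pearson columns fix the relapse and withdrawal risks as averages over all patients. The Spearman columns fix them at the average marker value, so the two Cox columns differ slightly.

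| Relapse by Week 192 | Pearson | Cox | Loss | Spearman | Cox | Loss |
|---|---|---|---|---|---|---|
| 10% | 12% | 28% | 57% | 16% | 35% | 54% |
| 20% | 25% | 51% | 51% | 32% | 56% | 43% |
| 30% | 41% | 66% | 38% | 51% | 72% | 29% |
| 50% | 71% | 87% | 18% | 73% | 89% | 18% |

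Over relapse risks of 10-50% and hazard ratios of 1.5-3.0, the Spearman loss runs from about 3% to 57%.

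Most of the loss comes from withdrawal. With no withdrawal, at 20% relapse and hazard ratio 2, power is 0.574 for Spearman and 0.628 for Cox, a loss of 1 − 0.574/0.628 = 9%. Dropping the censored patients is no remedy: correlating among relapsers only loses about 67-92% of the Cox power.

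**False positives when the marker has no effect on relapse.**

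| Relapse by Week 192 | Pearson, withdrawal HR 2 | Spearman, withdrawal HR 2 | Cox |
|---|---|---|---|
| 10% | 34% | 41% | about 5% |
| 20% | 24% | 32% | 5-6% |
| 30% | 20% | 24% | 5-6% |
| 50% | 14% | 16% | 5-6% |

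If withdrawal is unrelated to the marker (withdrawal HR 1), Pearson and Spearman both reject about 5% of the time. At a withdrawal HR of 1.5, Spearman rejects 8-15%.

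**Hidden or reversed association.** Take a marker that doubles the relapse hazard and halves the withdrawal hazard per SD. A harmful marker should correlate negatively with time. The mean Pearson r is about +0.11 at 10% relapse (reversed), 0.00 at 20% (lost) and −0.08 at 30% (right sign, but weak).

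**The case against.** The strongest reply is that the plan can be read in a way that removes the fault. The synopsis confines correlation to relations between biomarkers and sends efficacy objectives, of which time to first relapse is one, to regression. The statistical section also has a regression bullet, and the core study's regression for this kind of endpoint is Cox. The outcome list is illustrative, the word for correlation may be meant loosely, and details are left to a substudy SAP that is not among the documents (the SAP supplied covers the shorter infusion substudy only). The substudy is descriptive, about 50 patients strong, and the protocol does not expect significant results from it.

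Part of this stands. It limits the importance of the point, and it means that a censoring-aware regression is not excluded. A reader might infer that the protocol instructs analysts to treat censoring dates as relapse dates, or that no suitable model is planned. The documents say neither.

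It does not remove the point. The statistical section names correlation coefficients for clinical outcome in its own bullet, separate from the regression. An unnamed regression does not replace that bullet, and ordinary linear regression on recorded time would share the fault. The synopsis and the statistical section differ, which is itself a reason to correct the text. Deferral to a SAP fills in detail; it does not withdraw a method already named.

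It is also fair that Cox is weak here when relapses are few: at 10% relapse its power is only about 28-35%. The comparison is between the two methods, not with any design target.

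**Conclusion.** The point holds in a limited form. For time to first relapse, the named method cannot use the censoring information, although the main study already uses one that can.

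The loss of power relative to Cox is about half at an assumed 10-20% relapse and hazard ratio 2 per SD, falling to about 20% at 50% relapse. A reader might infer that half the power is lost in general. The documents do not support that, because they give no relapse risk, effect size or power.

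Bias from withdrawal is conditional. At a withdrawal hazard ratio of 2 per SD, Pearson gives 14-34% false positives, and a true association can be hidden or reversed when the marker pushes relapse and withdrawal in opposite directions. A reader might infer that the results will show who withdrew rather than who relapsed. That needs withdrawal to be related to the marker, which the documents do not establish; otherwise the error rate stays near 5%.

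No treatment or regulatory decision in the protocol depends on this analysis, so the correction is worth making but not critical.

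**What to change.** - In the second objective of Appendix 8 (synopsis and body), in its statistical section and in the substudy SAP, take time to first relapse and any other time-to-event core endpoint out of the correlation analysis. Analyse them with a censoring-aware model: Cox regression with the censoring rule of Section 6.4.1. A small-sample penalty such as Firth's is a reasonable option with so few events, but not essential.
- Keep correlation coefficients for relations between markers and for uncensored change scores such as EDSS, T1 volume and brain volume.
- Make the synopsis and the statistical section agree on whether correlation applies to clinical outcomes, and name the regression model for each type of outcome.

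The cost is about a sentence in each place. No new data, patients or assays are needed.
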